1.19	Timed Settling for Left Lens	
The investigator will start a stopwatch as soon as the left lens is inserted.
 
Note: All lenses in this study have scribe marks at 6 o'clock and 12 o'clock positions and rotation measurements are made relative to a vertical reference line.
 
Record base nasal or base temporal rotation to
	

		
the nearest degree.
 
At one (1) minute after insertion: Record:
 
 1. The rotational position to the nearest degree 
At three (3) minutes after insertion: Record:
 
 1. The rotational position to the nearest degree 	
1.20	Lens Settling	Allow the study lenses to settle for a minimum of 15 minutes.	
1.21	Toric Fit Evaluation	
After lens settling, record:
 
 • The rotational position to the nearest degree • Lens stability with blink • Lens stability with eye versions • Toric fit acceptable or unacceptable 
Toric lens fit will be unacceptable if lenses rotated more than 40 degrees, or lens stability is worse than 10 degrees movement with blink. If toric fit is unacceptable, remove the lenses, perform biomicroscopy and proceed to final evaluation.
 
Note: If unacceptable fit save the lenses and store in saline in glass vials labeled appropriately.
	████████
1.22	Subjective Lens Fit Assessment	
Evaluate overall lens fit acceptance (acceptable or unacceptable) based on centration, movement and other fitting characteristics.
 
An unacceptable fit is deemed by one of the following criteria:
 
 • limbal exposure at primary gaze or with extreme eye movement; • edge lift; • excessive movement in primary and up gaze; or • insufficient movement in all three of the following conditions: primary gaze, up gaze, and Josephson push up. 
If either lens is deemed unacceptable, the subject will be discontinued from the study. Perform a slit-lamp evaluation and complete the Final Evaluation.
	████████

		Note: If unacceptable fit save the lenses and store in saline in glass vials labeled appropriately.	
1.23	Post-Fit Questionnaire	The subject will respond to the PRO Post-Fit Questionnaire.	
1.24	Lens Removal	The Subject will remove the study lenses and store in saline in glass vials labeled appropriately.	
1.25	Removal Questions	The subject will respond to the removal questions.	

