8. SUBJECTS COMPLETION/WITHDRAWAL

8.1. Completion Criteria

Subjects are considered to have completed the study if they:

- provided informed consent;
- they are eligible;
- have not withdrawn/discontinued for any reason described in Section 8.2;
- Complete all study visits

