8.2. Withdrawal/Discontinuation from the Study

A subject will be withdrawn from the study for any of the following reasons:

- Subject death during the study period
- Subject withdrawal of consent
- Subject not compliant to protocol
- Subject lost to follow-up
- Subject no longer meets eligibility criteria (eg, the subject becomes pregnant)
- Subject develops significant or serious adverse events causing discontinuation of study lens wear
- Subjects who have experienced a Corneal infiltrative Event (CIE)
- Investigator's clinical judgment regarding the subject safety reasons (that it is in the best interest of the subject to stop treatment)
- Subject not compliant with study lens wear schedule
- Subject not successfully dispensed due to lack of efficacy and safety including poor vision, poor comfort or unacceptable fit

For discontinued subjects, the Investigator will:

- Complete the current visit (scheduled or unscheduled)
- Complete the Final Evaluation, indicating the reason that the subject was discontinued from the study
- Record the spherocylindrical refraction with best corrected distance visual acuity
- Collect used test article(s) (worn or brought to the visit) from the subject and discard them, unless otherwise stated in Section 7.2
- Collect all unused test article(s) from the subject

An additional subject may be enrolled if a subject discontinues from the study prematurely.

In cases where a subject is lost to follow-up, every possible effort must be made to contact the subject and determine the reason for discontinuation/withdrawal. The measures taken to follow up must be documented including two written attempts and a certified letter (or equivalent) as the final attempt.

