14. STATISTICAL METHODS

14.1. General Considerations

All data summaries and statistical analyses will be performed using the SAS software Version 9.4 (SAS Institute, Cary, NC). Throughout the analysis of data, the results for each subject/eye will be used when available for summarization and statistical analysis. Unscheduled visits will be summarized separately and will be excluded from the statistical analysis.

Summary tables (Descriptive statistics and/or frequency tables) will be provided for all baseline variables, efficacy variables and safety variables as appropriate. Continuous variables will be summarized with descriptive statistics (n, mean, standard deviation [SD], median, minimum and maximum). Frequency count and percentage of subjects or eyes within each category will be provided for categorical data.

Summaries will be presented by study lens type and will be performed separately by completion status. All analyses will be conducted on per-protocol population (see Section 14.3).

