14.3. Analysis Populations

Safety Population:

All subjects who were administered any test article excluding subjects who drop out prior to administering any test article. At least one observation should be recorded.

Per-Protocol Population:

All subjects who have successfully completed all visits and did not substantially deviate from the protocol as determined by the trial cohort review committee prior to database hard lock (Per-Protocol Population). Justification of excluding subjects with protocol deviations in the per-protocol population set will be documented in a memo to file.

Intent-to-Treat (ITT) Population:

All randomized subjects regardless of actual treatment and subsequent withdrawal from study or deviation from protocol. At least one observation should be recorded.

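### Per-protocol fit acceptability is 100% for all five lenses by construction, and no planned table shows the rate among all pairs fitted

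*Combined protocol and SAP*

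**What the plan says.** **Endpoint.** Lens fitting is the secondary endpoint (Synopsis; Section 2.2), and fitting characteristics on the eye are the secondary objective (Section 2.1). No single fit variable is named, and Section 2.3 attaches no hypothesis to fit.

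**Discontinuation.** Overall fit is judged for each pair at steps 1.22, 1.35, 2.14, 2.27 and 2.40. Each step carries the same rule: "If either lens is deemed unacceptable, the subject will be discontinued from the study". The toric fit step comes just before it (1.21, 1.34, 2.13, 2.26, 2.39). Toric fit is unacceptable with more than 40 degrees of rotation or more than 10 degrees of movement with blink. The lenses are then removed and the subject goes to biomicroscopy and the final evaluation.

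**Completion.** Section 8.2 lists as a withdrawal reason "Subject not successfully dispensed due to lack of efficacy and safety including poor vision, poor comfort or unacceptable fit". Section 8.1 requires that completers "have not withdrawn/discontinued for any reason described in Section 8.2".

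**Populations.** Section 14.3 defines the per-protocol set as "All subjects who have successfully completed all visits and did not substantially deviate from the protocol". The Safety Population is "All subjects who were administered any test article excluding subjects who drop out prior to administering any test article". Safety and ITT sets are both defined, but no analysis is assigned to either.

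**Analysis and tables.** Section 14.1 states "All analyses will be conducted on per-protocol population". It also says that summary tables "will be provided for all baseline variables, efficacy variables and safety variables as appropriate", and that "Summaries will be presented by study lens type and will be performed separately by completion status", with counts and percentages for categorical data.

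**The concern.** The set on which fit is to be analysed is defined partly by the fit result. A pair with an unacceptable overall fit removes its wearer, so the per-protocol set holds only subjects whose every pair fitted. In that set, acceptability cannot separate the five peripheral thicknesses, although describing how they fit is the secondary objective.

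At stake is a report showing 100% acceptability for all five lenses when one thickness may have failed more often. A reader would have to find a second table, of subjects selected largely because they failed, and combine the two.

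Safety summaries have a similar gap. A Grade 3 or higher slit-lamp finding after wear, or a corneal infiltrative event, also takes the subject out of the per-protocol set, and no table is assigned to the Safety Population.

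**Working it through.** **1. The chain.** Unacceptable overall fit in either eye → discontinued (7.2) → a listed withdrawal reason (8.2) → not a completer (8.1) → outside the per-protocol set (14.3) → outside all analyses (14.1). Section 8.2 speaks of dispensing in a non-dispensing study, but Section 5.3 counts a lens placed on the eye as dispensed, so the reason applies. A fifth-pair failure follows the same path: the subject has attended both visits, but step 2.40 discontinues them and 8.1 excludes them. If the rules are followed, per-protocol acceptability is 100% for each lens at any true failure rate.

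**2. Other fit measures.** Post-settling rotation and blink stability are cut at the 40- and 10-degree limits, because a toric failure also ends participation. Rotation at 1 and 3 minutes and stability with eye versions have no stated limit and can still differ between lenses.

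**3. Two readings of 14.1.** If the tables by completion status fall under the per-protocol sentence, the non-completer table is empty. If they stand apart from it, which is the natural reading, failures appear there with counts. Neither reading gives a table of everyone fitted.

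**4. What the planned tables would show.** The documents give no fit-failure rate, so the rates are assumptions. Take 100 subjects randomised over the ten Williams sequences (Section 5.1; each lens occurs twice in each period), exit at first failure, no other losses, no replacements and independent failures. Let p be the failure rate per pair and q = 1 − p. With the same p for every lens:

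- completers = 100q⁵
- failures per lens = 100(1 − q⁵)/5
- non-completer pairs per lens = 100 × Σ k·p·qᵏ⁻¹ / 5, for k = 1 to 5
- non-completer rate = failures / non-completer pairs
- all-fitted rate = failures / (non-completer pairs + completers)

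For p = 1%: completers 100 × 0.99⁵ = 95.1; failures 4.90/5 = 0.98; pairs 14.60/5 = 2.92; non-completer rate 0.98/2.92 = 33.6%; all-fitted 0.98/98.0 = 1.0%.

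For p = 1 − 0.8^(1/5) = 4.36%, the rate at which fit failure alone would explain the planned fall from 100 enrolled to 80 completing: completers 80.0; failures 20/5 = 4.00; pairs 58.2/5 = 11.64; non-completer rate 4.00/11.64 = 34.4%; all-fitted 4.00/91.6 = 4.4%.

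For 2% on four lenses and 10% on one: completers 100 × 0.98⁴ × 0.90 = 83.0. The 10% lens is reached with average probability (1 + 0.98 + 0.98² + 0.98³ + 0.98⁴)/5 = 0.961, giving 96.1 fitted, 9.61 failures and 13.1 non-completer pairs. Enumerating the ten sequences gives each 2% lens about 92.2 fitted, 1.84 failures and 9.2 non-completer pairs.

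| Assumed true failure rate | Per-protocol | Non-completers | All fitted |
|---|---|---|---|
| 1%, every lens | 0% | 33.6% | 1.0% |
| 4.36%, every lens | 0% | 34.4% | 4.4% |
| 2%, on four lenses | 0% | 20.0% | 2.0% |
| 10%, on the fifth lens | 0% | 73.5% | 10.0% |

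A more than fourfold difference in the true rate (first two rows) leaves both planned percentages almost unchanged.

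**5. If failures cluster within subjects.** A threshold model with a shared subject effect, at assumed latent correlations of 0.5 and 0.8, gives all-fitted rates of 3.2% and 2.2% for a true 4.4%. Failure-prone subjects leave early. At 0.8 the rate by period falls from 4.4% to 2.4%, 1.7%, 1.3% and 1.1%, and the non-completer rate is 41% for a true 1% and 45% for a true 4.4%.

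**The case against.** The strongest reply is that the failures are already reported. Section 14.1 promises by-lens counts for non-completers, and a reading that leaves that table empty makes the sentence pointless. In the 4.36% example, 4.00 failures among 11.64 non-completer pairs plus 80.0 completers gives 4.4%, exactly the rate asked for. The gap is then a missing pooled row for a descriptive endpoint without a hypothesis, in a study described as an initial evaluation. This largely stands and limits the severity. What remains is that the plan does not call for the addition, and neither percentage it does plan shows the rate.

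Four stronger readings are tempting, and the documents do not support them:

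- A reader might infer that unacceptable fits vanish from the report. On the natural reading of 14.1 they do not.
- A reader might infer that the whole secondary endpoint is uninformative. Lens fitting is not reduced to acceptability, and measures without a stated limit can still differ among completers.
- A reader might infer that overall acceptability exists for every pair. It need not: a toric failure sends the subject to the final evaluation before overall fit is judged, so a pooled table must say how such pairs count.
- A reader might infer that the handling comparison is biased by the same exclusion. Nothing shown here establishes that, and this point makes no claim about it.

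**Conclusion.** The point holds for overall fit acceptability and, as truncation, for post-settling rotation and blink stability. The per-protocol 100% follows from the text and depends on no assumed rate, provided sites apply the discontinuation rule. A subject kept on against the rule would be a deviation for the cohort review committee to judge.

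How far the planned percentages mislead does rest on assumptions: the failure rates, exit at first failure, and no other losses or replacements. Under independence the non-completer figure is about 34% for a true rate of either 1% or 4.4%. The 4.4% is not a forecast; it attributes all planned attrition to fit.

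Severity is minor to should-fix. The endpoint is descriptive, carries no hypothesis, and its all-fitted rate can be recovered by hand, but the correction is cheap.

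**What to change.** In Section 14.1, limit the per-protocol sentence to the CLUE handling analyses and add wording along these lines:

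> Lens fit will be summarised descriptively by lens type in the Safety Population, completers and non-completers together, with counts and denominators per pair fitted, overall and by period. A pair is a fit failure if toric fit or overall fit is unacceptable in either eye. Toric and overall fit will also be shown separately, with the number of pairs in which overall fit was not assessed because toric fit had already failed. Adverse events and slit-lamp findings will be summarised in the Safety Population.

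Tables by completion status can stay as supplementary. The clinical discontinuation rules do not change. Sections 14.3 and 14.6 need no change for this purpose: 8.1 and step 2.40 already settle fifth-pair failures of overall fit.

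The cost is a few sentences, pooled fit and safety tables, and one by-period table. No new data are needed, since the toric result is recorded before exit and the Safety Population is already defined.

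There are two downsides. Fit and handling will have different denominators. And because subjects exit at the first failure, the all-fitted rate is too low if failures cluster within subjects. The by-period table would show this, but imprecisely for a single lens: with 100 subjects, the first period has 20 pairs per lens, and at a 4.36% rate the standard error is √(0.0436 × 0.9564/20) = 4.6 percentage points.

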7.3 Unscheduled Visits

If, during the investigation, a subject requires an unscheduled visit to the clinical site, the following information will be collected at a minimum:

- Chief complaint prompting the visit. If the reason is an adverse event, the applicable eCRF for the adverse event must be completed and subject record completed as appropriate
- Date and time of the visit and all procedures completed at the unscheduled visit
- Review of adverse event and concomitant medications
- Documentation of any test article dispensed or collected from the subject, if applicable
- Slit lamp findings (using the Slit Lamp Classification Scale)

If the Investigator withdraws a subject from the study, the final study visit case report forms must be completed indicating the reason(s) why the subject was withdrawn. The subject record must be completed documenting the date and primary reason for withdrawal and the study CRA notified.

Any ocular and non-ocular Adverse Events that are ongoing at the time of the study visit will be followed by the Investigator, within licensure, until they have resolved, returned to pre-treatment status, stabilized, or been satisfactorily explained. If further treatment ie, beyond licensure is required, the subject will be referred to the appropriate health care provider.

The following information will be collected during an unscheduled visit.

Step	Procedure	Details	
U.1	Chief Complaints	Record the subject's chief complaints for reasons for the unscheduled visit	
U.2	Change of Medical History and Concomitant Medications	Questions regarding the change of subjects' medical history and concomitant medications.	
U.3	Subject Reported Ocular Symptoms	Subjects will respond to a verbal open-ended symptoms questionnaire.	
U.4	Entrance VA	Record the entrance distance visual acuity (OD, OS and OU) to the nearest letter.	
U.5	Subjective Sphero-cylindrical Refraction	An optimal, binocular balanced distance sphero-cylindrical refraction will be performed. Record the refraction and distance visual acuity to the nearest letter.	
U.6	Biomicroscopy	FDA Slit Lamp Classification Scale will be used to grade the findings and determine eligibility. For the conjunctival redness [REDACTED] 0.5 unit increments will be used in the grading. Corneal Staining Assessment [REDACTED] will be graded in 1.0 increments. If any of these slit lamp findings are Grade 3 or higher, the subject will be discontinued. If discontinued a final examination must be completed. If the clearance of the fluorescein needs to be expedited, preservative-free rewetting drops or saline may be instilled.	
U.7	Exit Visual Acuity	Record the subject's exit distance visual acuity (OD, OS and OU) to the nearest letter.	

7.4 Laboratory Procedures

Not Applicable.

8. SUBJECTS COMPLETION/WITHDRAWAL

8.1. Completion Criteria

Subjects are considered to have completed the study if they:

- provided informed consent;
- they are eligible;
- have not withdrawn/discontinued for any reason described in Section 8.2;
- Complete all study visits

8.2. Withdrawal/Discontinuation from the Study

A subject will be withdrawn from the study for any of the following reasons:

- Subject death during the study period
- Subject withdrawal of consent
- Subject not compliant to protocol
- Subject lost to follow-up
- Subject no longer meets eligibility criteria (eg, the subject becomes pregnant)
- Subject develops significant or serious adverse events causing discontinuation of study lens wear
- Subjects who have experienced a Corneal infiltrative Event (CIE)
- Investigator's clinical judgment regarding the subject safety reasons (that it is in the best interest of the subject to stop treatment)
- Subject not compliant with study lens wear schedule
- Subject not successfully dispensed due to lack of efficacy and safety including poor vision, poor comfort or unacceptable fit

For discontinued subjects, the Investigator will:

- Complete the current visit (scheduled or unscheduled)
- Complete the Final Evaluation, indicating the reason that the subject was discontinued from the study
- Record the spherocylindrical refraction with best corrected distance visual acuity
- Collect used test article(s) (worn or brought to the visit) from the subject and discard them, unless otherwise stated in Section 7.2
- Collect all unused test article(s) from the subject

An additional subject may be enrolled if a subject discontinues from the study prematurely.

In cases where a subject is lost to follow-up, every possible effort must be made to contact the subject and determine the reason for discontinuation/withdrawal. The measures taken to follow up must be documented including two written attempts and a certified letter (or equivalent) as the final attempt.

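### Sections 7.2 and 8.2 conflict on what a subject completes after a failed lens fit, and the 7.2 order leaves that pair's handling score uncollected

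*Combined protocol and SAP*

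**What the plan says.** Section 7.2 gives each of the five lens pairs the same sequence. The subject inserts the lenses and lets them settle for at least 15 minutes. The investigator then judges toric fit (step 1.21) and overall fit (step 1.22). Only after that does the first questionnaire appear, at step 1.23: "The subject will respond to the PRO Post-Fit Questionnaire". The subject then removes the lenses (1.24) and answers the Removal Questions (1.25).

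Each fit step has its own exit. For toric fit: "If toric fit is unacceptable, remove the lenses, perform biomicroscopy and proceed to final evaluation". For overall fit: "If either lens is deemed unacceptable, the subject will be discontinued from the study. Perform a slit-lamp evaluation and complete the Final Evaluation". The same text recurs for every later pair.

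Section 8.2 counts the same event as a withdrawal: "Subject not successfully dispensed due to lack of efficacy and safety including poor vision, poor comfort or unacceptable fit". Its list of duties for discontinued subjects opens with "Complete the current visit (scheduled or unscheduled" and gives the Final Evaluation as a separate item.

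**The concern.** A site that follows Section 7.2 as ordered leaves at the fit step and does not give either questionnaire. A site that follows Section 8.2 finishes the visit and gives both. The two sites would record different data for the same event.

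The item at stake is the CLUE handling score, the primary endpoint in Section 2.2. By the time of the fit check the subject has inserted the pair and worn it for about 15 minutes, which is the exposure named in the Section 2.3 hypotheses. If the score is missing, it is missing because of how that lens behaved on the eye. Lens fitting is the secondary endpoint, and peripheral thickness, the factor under study, may affect it. Missingness of that kind is hard to treat as unrelated to lens type, and the score cannot be obtained later.

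**Working it through.** No figure in the plan is in dispute, so the check sets the passages side by side and counts scores.

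**1. Does Section 8.2 cover fit failures?** Yes, by its own list of reasons. It gives way to Section 7.2 in one place only, on used lenses: "discard them, unless otherwise stated in Section 7.2". That exception is not attached to completing the visit.

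**2. Step order and scores available.** If fit fails at pair k, the 7.2 order leaves k−1 study-lens handling scores. Section 8.2 leaves k if read as finishing that pair. If read as finishing the visit it leaves 2 (Visit 1, pairs 1–2) or 5 (Visit 2, pairs 3–5).

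| Pair k | Fit checks | Questionnaires | 7.2 order | 8.2, this pair | 8.2, whole visit |
|---|---|---|---|---|---|
| 1 | 1.21, 1.22 | 1.23, 1.25 | 0 | 1 | 2 |
| 2 | 1.34, 1.35 | 1.36, 1.38 | 1 | 2 | 2 |
| 3 | 2.13, 2.14 | 2.15, 2.17 | 2 | 3 | 5 |
| 4 | 2.26, 2.27 | 2.28, 2.30 | 3 | 4 | 5 |
| 5 | 2.39, 2.40 | 2.41, 2.43 | 4 | 5 | 5 |

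The 7.2 count differs from both 8.2 counts in every row.

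**3. Could the score come from elsewhere?** No. The Final Evaluation holds refraction with acuity (F.1) and disposition (F.2). The Baseline Questionnaire (step 1.7) concerns habitual lenses. The study questionnaires in Appendix A were not available for this review, so which form carries the CLUE handling items could not be checked. Both forms come after both exits, so the answer does not depend on it.

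**4. Which analyses would use the score?**
- *Primary analysis.* Section 14.1 puts all analyses on the per-protocol population, which Section 14.3 limits to subjects who successfully completed all visits. Section 8.1 does not count anyone withdrawn for a Section 8.2 reason as a completer. A fit failure is therefore left out whether or not the score is collected.
- *Summaries.* Section 14.1 also asks for summaries by lens type, separately by completion status. Non-completers' scores would appear there.
- *Missing-data sensitivity analysis.* Section 14.9 calls for multiple imputation if dropout exceeds 15%. Planned attrition is (100 − 80)/100 = 20%, which passes that trigger if all of it is dropout. Section 14.9 does not name the analysis set. To examine dropout it must include subjects whom the per-protocol set removes.
- *ITT.* Section 14.3 defines the set, but no analysis is assigned to it. Any that is run would be affected.

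**5. Size.** The number of scores lost is one per failed fit when 8.2 is read as finishing the pair. The documents give no fit-failure rate and no link between fit failure and handling score, so no shift in CLUE points can be calculated.

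**The case against.** **The conflict may be softer than it looks.** Section 8.2 is one general list for every discontinuation, including death and loss to follow-up. Read literally, it could have a discontinued subject fitted with the visit's remaining pairs. A sensible site might take it to mean closing out the visit forms, with the specific steps of 7.2 governing. That reading is reasonable, but the text does not state it, and the one explicit deferral to 7.2 lies elsewhere in the same list. It would also settle the conflict in favour of the order that omits the score.

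**The overall-fit exit is less explicit.** Step 1.22 does not say to skip the questionnaires. The toric exit is firm; the overall-fit exit omits the questionnaires by sequence only. This stands, and it is a further reason why sites may differ.

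**Part of the score may not exist at the fit check.** Removal Questions follow removal, and step 1.21 does not say who removes the lenses. This also stands. It bears on how the correction is worded, not on whether one is needed.

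**Two stronger readings are tempting.**
- *That the primary estimate is biased by a known amount.* A reader might multiply an assumed 10% loss by an assumed 10-point gap to get 0.10 × 10 = 1.0 point, a fifth of the 5-point margin. The documents support neither input. Control pairs can fail too, which pushes the other way. The planned loss of 20 in 100 from all causes, spread evenly over five lenses, would be 20%/5 = 4% per lens. Above all, the per-protocol estimate leaves these subjects out under either section.
- *That a subject whose first pair fails drops out of the ITT set.* Section 14.3 asks only this: "At least one observation should be recorded". It does not say of what. Rotation readings at one and three minutes and the fit result would already be on record and could satisfy it.

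**Conclusion.** The contradiction is real for all five pairs. Followed in its stated order, Section 7.2 loses the handling score of the pair just worn, for a reason tied to that lens.

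The consequence is limited. The conflict alone does not move the planned per-protocol primary estimate. It weakens the analyses meant to show whether leaving out non-completers matters: imputation would have to fill in scores that could have been collected, under a model that does not know why they are absent. How much this matters depends on the unstated fit-failure rate and on whether fit varies with thickness, which the documents do not settle.

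The conclusion assumes that per-protocol completion is read through Section 8.1. No position is taken on whether a fit failure should lead to discontinuation.

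**What to change.** 1. Reconcile Sections 7.2 and 8.2, and state which governs after a failed fit. The sponsor chooses the exit rule.
2. At steps 1.21 and 1.22 and their repeats, add one sentence: whichever exit rule is kept, the Post-Fit Questionnaire and Removal Questions for the pair just worn are completed before the Final Evaluation. Record who removed the lenses, so that the removal answers can be interpreted.
3. In Section 14, add a mixed-model analysis of all randomised subjects with any study-lens handling score, using the Section 14.5 model and reported beside the per-protocol analysis. Name the set on which the Section 14.9 imputation is run.

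The cost is a few minutes per failed fit, one sentence at each fit step and one additional analysis, with no extra staff or visit. The change has limits. Scores for pairs never tried stay missing, and a subject discontinued before wearing the Control lens gives no within-subject difference. It reduces selective missingness but does not remove it.
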